4.0 Study Intervention(s)/Investigational Agent(s)

4.1 Description: Subjects will be randomized to one of three experimental marketplaces (20 subjects in each condition): 1) a condition simulating a ban on menthol cigarettes but not menthol e-cigarettes (condition A); 2) a condition simulating a ban on both menthol cigarettes and menthol e-cigarettes (Condition B); and 3) a condition in which menthol is not banned for either product (Condition C – the control condition). All conditions would have medicinal nicotine available if subjects decide to quit tobacco products entirely.

The goal of the experimental marketplace is to provide a context in which product preferences can be evaluated in a systematic way but with a high degree of ecological validity. We have therefore included in the marketplace both a

cigarette-like e-cigarette system and a tank-like e-cigarette system (which has the potential to deliver higher doses of nicotine), as those are the two most commonly used e-cigarette systems currently available.

Products available to subjects in each experimental marketplace		
Condition A (menthol ban for cigs)	Condition B (menthol ban for cigs and e-cigs)	Condition C (no menthol ban)
- Non-menthol cigarettes	- Non-menthol cigarettes	- Menthol & non-menthol cigarettes
- Menthol & tobacco flavored versions of commonly used cigarette-like e-cigarette (e.g., Vuse)	- Tobacco flavored version of commonly used cigarette-like e-cigarette (e.g., Vuse)	- Menthol & tobacco flavored versions of commonly used cigarette-like e-cigarette (e.g., Vuse)
- Menthol & tobacco flavored versions of commonly used tank-like e-cigarette (e.g., Joyetech eGo AIO)	- Tobacco flavored version of commonly used tank-like e-cigarette (e.g., Joyetech eGo AIO)	- Menthol & tobacco flavored versions of commonly used tank-like e-cigarette (e.g., Joyetech eGo AIO)
- Nicotine gum and lozenge (various flavors)	- Nicotine gum and lozenge (various flavors)	- Nicotine gum and lozenge (various flavors)

We will include the subject's usual brand of cigarettes in the marketplace (either the non-menthol version or both the non-menthol and menthol version depending on the randomization). Information about their usual brand will be collected at the screening visit in order to incorporate it into the marketplace.

4.2 Drug/Device Handling: The tobacco and nicotine replacement products that will be provided to subjects are marketed products and are not required to be dispensed by a physician or licensed pharmacy. They will be provided to participants by the study coordinator

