Studies that have specifically examined menthol flavoring in e-cigarettes include a study in which African American menthol smokers could select using either menthol or tobacco flavored e-cigarettes (or nicotine gum) for a two week quit

attempt. This study found that 74% selected menthol flavored e-cigarettes.²⁸ A study designed specifically to examine the role of flavor on smoking patterns asked smokers to abstain from cigarettes and only use an assigned flavor of e-cigarettes. This study found that those assigned to menthol flavored e-cigarettes had the largest decrease in number of cigarettes smoked relative to those assigned to tobacco, cherry, or chocolate flavored e-cigarettes.¹³ In an additional cross-over study, twenty non-treatment seeking smokers used menthol and tobacco flavored e-cigarettes, each for 7 – 10 days and completed on their last day of e-cigarettes use, a laboratory session at which they used their assigned product for 5 minutes. In female smokers who used their non-preferred flavor (i.e., menthol smokers using non-menthol e-cigarettes and vice versa), nicotine concentrations were lower and the e-cigarette was rated as less likeable than when using their preferred flavor with no such differences found in men.²⁹ These studies suggest that menthol cigarette smokers prefer menthol flavored e-cigarettes, that menthol flavored e-cigarettes have the potential to decrease smoking to a greater extent than other e-cigarette flavors and that there may be sex differences in response to menthol flavoring in e-cigarettes. The current study will build on this research by providing preliminary data into how availability of e-cigarettes affects cigarette smoking and if these effects are moderated by the availability of menthol flavored cigarettes and / or e-cigarettes.

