5.2.3 Evaluation Visits (3 visits occurring at 2 week intervals). Subsequent to the baseline visit, subjects will be evaluated at 3 visits occurring at two week intervals (i.e., at approximately 2, 4 and 6 weeks after the baseline visit). To each visit, subjects will be asked to bring back any unused product as well as all used and unused e-cigarette cartridges or e-fluid vials. The cartridges and vials will be weighed prior to distribution and after use to determine the extent to which they were used. Participants will be allowed to keep any of the unused products so as to not discourage them from bringing back unused product.

At each visit, exhaled carbon monoxide concentrations will be measured and subjects will complete questionnaires assessing various aspects of smoking behavior including craving, withdrawal symptoms and motivation to quit smoking. Questionnaires assessing how they rate the effects of the products they are using and their perceived health risks of using these products will also be assessed. A food diary asking primarily about dietary menthol will be completed to determine if dietary intake changes occur if menthol in tobacco products is no longer available. Level of support for a ban on a variety of menthol containing tobacco products will be evaluated at the baseline and week 6 visits.

Additionally, at the week 6 visit urine will be collected in order to measure cotinine concentrations. At each visit (except for the week 6 visit), subjects will again have the opportunity to obtain additional products for the subsequent 2 weeks using their available credits. They may choose to obtain any of the available products in their marketplace and are not limited to products that they had previously chosen.

5.3 Individually Identifiable Health Information: All information is collected directly from subjects (i.e., medical records will not be requested) and this is not a treatment study. The data being collected therefore does not meet the definition of PHI.

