9.0 Study Population

9.1 Inclusion Criteria: To be eligible subjects must:

- a) Be between the ages of 21 and 64
- b) Smoke (on average) at least 5 cigarettes per day over the past year
- c) Purchase exclusively menthol cigarettes
- d) Not currently motivated to quit smoking
- e) Able to receive daily text or email survey reminders and follow the link provided to complete the online RedCap surveys

9.2 Exclusion Criteria: Subjects will be excluded if they:

- a) Report a serious, unstable medical or psychiatric condition
- b) Have a history of substance abuse (other than nicotine) within 3 months of beginning the study
- c) Use any medications that might interfere with measures to be studied (for example, medications known to affect smoking)

- d) Have used any smoking cessation therapy during the past month
- e) Regularly use any form of tobacco other than cigarettes (> 9 times per month)
- f) Are pregnant or breast feeding or planning to become pregnant or breast feed during the study
- g) Currently participating in other clinical research studies

9.3 Screening: At the screening visit, subjects will complete a series of questionnaires including those that ask about medical history, smoking history, and motivation to quit smoking. All inclusion / exclusion will be based on self-report except for smoking status which will be confirmed via an exhaled carbon monoxide (CO) concentration of ≥ 8 ppm or a urinary nicotine test strip reading of 6. Non-pregnant status will be confirmed via a urine pregnancy test.

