16.0 Data Management

16.1 Data Analysis Plan: Means (arithmetic or geometric for log-transformed variables) and their corresponding confidence intervals will be calculated for each study condition. Results will also be tabulated separately for men and women. A linear mixed model will be fit for each outcome variable, with fixed categorical effects of group, time, and their interaction, and random subject effects to account for correlation among repeated measurements on the same subject. We expect randomization to balance groups with respect to important baseline covariates such as cigarettes smoked per day and degree of nicotine dependence; however, we will check this assumption using ANOVA and consider adjustment for imbalanced factors. Exploratory modeling of gender and race / ethnicity effects will also be performed. Model contrasts will be used to evaluate the hypotheses of the two aims, primarily that cigarettes smoked will be lower and e-cigarette use higher when menthol e-cigarettes are available (Aim 1: conditions A and C compared to B), and that these effects will be larger when menthol cigarettes are unavailable (Aim 2: condition A compared to C)

16.2 Power Analysis: The main purpose of this project is to provide initial information regarding how banning menthol in either only cigarettes or in both cigarette and e-cigarettes will influence tobacco use patterns so as to better design a subsequent study that more definitively addresses this issue. This study will also provide feasibility information regarding using an experimental marketplace for assessing this question. For this pilot study, we plan on recruiting 60 subjects and anticipate (assuming 10% dropout), that there would be 18 evaluable subjects per group. If there is a large effect, we should be able to detect it as this sample size will provide 80% power for a between-groups time-averaged effect size of 0.8, assuming two-sided alpha=0.05 and within-subject autocorrelation of 0.6.

16.3 Data Integrity: In order to ensure that data entry is correct, data collected on paper questionnaires will be entered twice with the two entries compared and any discrepancies resolved.

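### No stratification is described, and Section 16.1 only considers adjusting for chance imbalance; sex and prior e-cigarette use should be prespecified covariates

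*Combined protocol and SAP*

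**What the plan says.** Section 4.1 states that "Subjects will be randomized to one of three experimental marketplaces (20 subjects in each condition"). Neither it nor Section 5.1 describes how the sequence is generated, or any blocks or strata.

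On sex, Section 2.3 concludes from the cited studies that "there may be sex differences in response to menthol flavoring in e-cigarettes". Section 16.1 adds that "Results will also be tabulated separately for men and women" and plans exploratory modelling of gender.

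On prior vaping, Section 9.2 excludes those who "Regularly use any form of tobacco other than cigarettes (> 9 times per month"). Occasional e-cigarette users below that limit can therefore enter. The amount of each product used per week is the primary outcome (Section 3.1).

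On imbalance, Section 16.1 expects randomisation to balance important covariates, giving cigarettes per day and nicotine dependence as examples. It will check this with ANOVA and consider adjusting for factors found to be unbalanced. Prior e-cigarette use is not named.

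**The concern.** Occasional vaping at entry could plausibly predict how much a person vapes during the study, and the protocol itself raises sex as a possible modifier of the response to flavour. With 20 per arm, chance can leave noticeable gaps on either factor.

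The safeguard in Section 16.1 is weak in two ways. Adjustment hangs on a baseline significance test that has little power at this size, and even after that test it is only considered. The final model therefore depends on the data and on a later judgement. At stake are some precision and a clear reading of the arm differences that are meant to inform the next study.

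**Working it through.** **1. The plan's own figure.** Section 16.2 gives "assuming 10% dropout), that there would be 18 evaluable subjects per group" (60 × 0.9 / 3 = 18) and says "this sample size will provide 80% power for a between-groups time-averaged effect size of 0.8", "assuming two-sided alpha=0.05 and within-subject autocorrelation of 0.6". Section 5.2.3 says "subjects will be evaluated at 3 visits occurring at two week intervals". With m = 3 measurements and a constant correlation of 0.6, the variance factor is (1 + 2 × 0.6)/3 = 0.733. The standard error of a two-arm difference is sqrt(0.733 × 2/18) = 0.285 SD. Power is Φ(0.8/0.285 − 1.96) = 0.80, so the stated 80% reproduces.

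**2. Chance of imbalance.** Suppose k of the 60 participants have a factor and allocation is an unstratified 20/20/20 split. Then P(a, b, c) = C(20,a) C(20,b) C(20,c) / C(60,k), with a + b + c = k. The documents give no value of k for either factor, so these are assumptions. Exact chances of a gap of 25 percentage points or more:

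| Factor (k of 60) | Some pair of arms | A vs C | A+C vs B |
|---|---|---|---|
| Women, 30 | 35.3% | 15.7% | 5.4% |
| Women, 24 or 36 | 33.8% | 14.9% | 4.9% |
| Occasional vapers, 6 | 4.0% | 1.4% | 0.1% |
| Occasional vapers, 12 | 19.3% | 7.6% | 1.4% |
| Occasional vapers, 18 | 28.9% | 12.3% | 3.4% |
| Occasional vapers, 24 | 33.8% | 14.9% | 4.9% |

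The last two columns are the contrasts named in Section 16.1 for Aim 2 and Aim 1. With 30 women, for example, the Aim 1 gap is (30 − b)/40 − b/20 = 0.75 − 3b/40, which reaches 25 points in size only if b ≤ 6 or b ≥ 14.

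**3. Would the ANOVA check catch it?** Take 13, 8 and 9 women in the three arms, a 25-point gap. The between-arm sum of squares is (3² + 2² + 1²)/20 = 0.7, the total is 60 × 0.25 = 15, and the within-arm sum is 14.3. F = (0.7/2)/(14.3/57) = 1.40 on 2 and 57 df, so p = (1 + 2 × 1.40/57)^(−57/2) ≈ 0.26. The check would pass.

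**4. Cost of leaving a predictive factor out.** If a factor with prevalence p shifts the outcome by d SD (SD of the time-averaged outcome among people alike on that factor), the unadjusted standard error is larger by sqrt(1 + p(1 − p)d²). For p = 0.3:
- d = 0.5: sqrt(1 + 0.21 × 0.25) = 1.026, about 3%.
- d = 1: sqrt(1 + 0.21) = 1.10, 10%.

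The values of d are assumptions.

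**5. What stratification adds once both factors are in the model.** In simulations of 54 analysed people (50% women, 30% vapers), unstratified allocation gave an adjusted standard error about 2% larger than blocks of 3 in four strata, for both planned contrasts. With such blocks the arms differ by at most 2 women and at most 2 vapers when randomised, because each level of a factor spans two strata and each unfinished block adds a difference of at most 1. Total arm sizes differed by about 1.5 on average and by at most 4.

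**The case against.** The strongest reply is that this is a pilot, that randomisation protects the type I error whatever the chance imbalance, and that the plan is not silent: it has a balance check, possible adjustment, tables by sex and exploratory gender modelling. Daily product surveys also start before baseline (Section 5.2.1), so prior vaping is measured. All of that stands, and it limits the weight of the point. It does not remove it, because the plan commits to none of these data as covariates and step 3 shows how little the check detects.

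Three stronger readings are tempting, and the documents do not support them.

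- *Marked imbalance is likely.* This needs a lower threshold, any of three pairs and either of two factors together. With 50% women and 10-30% vapers, treated as independent, a gap of 20 points or more somewhere has a 58-72% chance. At 25 points, on the contrasts the plan will test, it is a minority event for each factor. The only vaping prevalences in Section 2.1 (5.5% of adults, 8.9% of young adults) are not figures for smokers, but they warn against assuming only high values.
- *A chance gap is bias on top of the standard error.* A 25-point gap on a factor worth 0.5-1 SD moves an unadjusted contrast by 0.13-0.25 SD. Under randomisation that movement is already part of the variance behind the standard error.
- *The protocol expects women to vape more.* Section 2.3 says only that there may be sex differences. The cited crossover study of twenty smokers found lower nicotine concentrations and liking in women using their non-preferred flavour. That is an interaction of sex with flavour, not a higher level of vaping in women.

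**Conclusion.** The point holds as a gap in prespecification. No stratification is described, two factors the protocol itself makes relevant are left to chance, and the handling of imbalance is data-dependent and omits prior e-cigarette use. Validity is not threatened.

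The cost is an unadjusted standard error about 3-10% larger than necessary for e-cigarette use, if 30% vape occasionally and this shifts use by 0.5-1 SD, together with arm differences that are harder to interpret if a gap occurs. If prior vaping is rarer or less predictive, the loss is smaller. Nearly all the gain comes from prespecified adjustment. Severity is minor to moderate.

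**What to change.** In Section 16.1, replace the ANOVA check and the option to adjust with a commitment: every model includes fixed effects for sex and for baseline e-cigarette use, defined either as any use in the past month (recorded at screening) or as use on the daily surveys before baseline. If the survey measure is used, state that the same baseline value is not also an outcome time point in the e-cigarette model. Sex-by-condition effects can stay exploratory; a main effect of sex does not test them.

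The cost is two model terms and at most one added screening question. This can still be done if enrolment has begun, provided it is fixed before the outcome data are examined by arm.

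Optionally, if enrolment has not begun, state in Section 4.1 that allocation is 1:1:1 in permuted blocks stratified by the same two factors, using the past-month definition. That needs a stratified list in place of a single list. With blocks of 3, arm sizes may differ by about 2, and occasionally by up to 4. The further reduction in standard error is only about 2%, so this is a refinement and not a requirement.

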4.3 IND/IDE. N/A

4.4 Biosafety: N/A

5.0 Procedures Involved

5.1 Study Design: This is a pilot study in which over a 6 week period, menthol cigarette smokers will receive all of their tobacco products from a simulated experimental marketplace. Smokers will be assigned to one of three marketplace conditions: 1) a condition simulating a ban on menthol cigarettes but not menthol e-cigarettes; 2) a condition simulating a ban on both menthol cigarettes and menthol e-cigarettes; and 3) a condition in which menthol is not banned for either product (i.e., the control condition). All conditions would have medicinal nicotine available if subjects decide to quit tobacco products entirely. Subjects would receive "credits" that they can exchange, at visits occurring every two weeks, for any product available in their randomized marketplace condition. At the end of the experimental period any unused credits can be exchanged for monetary payment.

5.2 Study Procedures: The following procedures will occur during the study.

5.2.1 Screening Visit: Initial eligibility will be assessed via a phone interview or online screening form housed on REDCap. All screened participants will be notified by phone or email regarding their eligibility to be scheduled for a screening visit at which written informed consent will be obtained and eligibility

confirmed. At the screening visit, medical and psychiatric history will be obtained via subject report. Women will have a urine pregnancy test to confirm that they are not pregnant. A medical professional (e.g., Nurse Practitioner) will review medical histories to ensure eligibility. Baseline questionnaires assessing smoking history will be administered and an exhaled carbon monoxide (CO) will be measured to confirm smoking ($CO \geq 8$ ppm). A NicCheck using a urine sample will be performed (with a cut-off = 6 for those who otherwise qualify but for whom CO is < 8 ppm (e.g., they didn't smoke that morning, they came straight from work, etc.). Subjects who qualify and are interested in continuing will be invited to return to the baseline visit.

After eligibility is confirmed, subjects will begin receiving links daily via either text message or email (whichever they prefer) to a tobacco use survey that is to be completed on RedCap. On this survey subjects will report use of all tobacco and nicotine containing products used during the past day. These survey will continue until the end of the subject's participation in the study.

5.2.2 Baseline Visit (i.e., week 0): At the baseline visit, urine will be collected from which baseline urinary cotinine concentrations will be measured. Exhaled CO will be measured from a breath sample. Tobacco use behavior subsequent to the screening visit will be determined as will subjects' level of craving, withdrawal, motivation and self-efficacy to quit smoking and support for a ban on a variety of menthol containing tobacco products. Degree of nicotine dependence will be assessed using the Fagerstrom Test for Nicotine Dependence.³⁰ Subjects will be informed which products are available in the marketplace that they have been randomized to and will be allowed to handle each of the products and examine the packaging that each normally comes in.

Subject will be given credits at each visit that can be exchanged for products in their marketplace. All products will be discounted to approximately 66% of the retail market value (similar to the study summarized in preliminary data) in order to discourage subjects from purchasing products outside the marketplace and also prevent hoarding credits for payment at the end of the study. The credit amount will be calculated in order to allow on average a 1 pack/day smoker to replace all of their tobacco products based on normal usage patterns (e.g., for example, one cartridge of Vuse lasts about as long as one pack of cigarette). In order to discourage subjects obtaining more products than they need, any credits not used at each visit can be banked and used at later visits or converted to monetary payment at the end of the study. Subjects will be informed that they can obtain any amount or type of product up to the value of current and banked credits and will be provided with the packaging that normally accompanies these products. Instructions for product use will be primarily limited to what is on the packaging so as to more accurately simulate natural marketplace conditions; however subjects can ask questions about the products to which accurate answers will be provided. While subjects will be encouraged to obtain all tobacco products they use from the experimental marketplace, no penalties will be levied for outside purchases in order to encourage truthful reports of noncompliance.

5.2.3 Evaluation Visits (3 visits occurring at 2 week intervals). Subsequent to the baseline visit, subjects will be evaluated at 3 visits occurring at two week intervals (i.e., at approximately 2, 4 and 6 weeks after the baseline visit). To each visit, subjects will be asked to bring back any unused product as well as all used and unused e-cigarette cartridges or e-fluid vials. The cartridges and vials will be weighed prior to distribution and after use to determine the extent to which they were used. Participants will be allowed to keep any of the unused products so as to not discourage them from bringing back unused product.

At each visit, exhaled carbon monoxide concentrations will be measured and subjects will complete questionnaires assessing various aspects of smoking behavior including craving, withdrawal symptoms and motivation to quit smoking. Questionnaires assessing how they rate the effects of the products they are using and their perceived health risks of using these products will also be assessed. A food diary asking primarily about dietary menthol will be completed to determine if dietary intake changes occur if menthol in tobacco products is no longer available. Level of support for a ban on a variety of menthol containing tobacco products will be evaluated at the baseline and week 6 visits.

Additionally, at the week 6 visit urine will be collected in order to measure cotinine concentrations. At each visit (except for the week 6 visit), subjects will again have the opportunity to obtain additional products for the subsequent 2 weeks using their available credits. They may choose to obtain any of the available products in their marketplace and are not limited to products that they had previously chosen.

5.3 Individually Identifiable Health Information: All information is collected directly from subjects (i.e., medical records will not be requested) and this is not a treatment study. The data being collected therefore does not meet the definition of PHI.

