2.2 Preliminary Data: Our research team has considerable experience with the methods proposed in this study and with the study population being recruited. The most relevant projects include:

2.2.1 Data demonstrating that in the event of a menthol ban in cigarettes, smokers of menthol cigarettes switch to smoking non-menthol cigarettes: In a pilot study led by [name], we asked African American menthol cigarette smokers to not smoke menthol cigarettes for a 4 week period in order to obtain information regarding how they would adjust their smoking behavior were menthol cigarettes not available (as in the event of a ban).¹⁷ No specific instructions were provided regarding how to cope with abstaining from menthol cigarettes. Of the 32 subjects who completed the study, three reported making a quit attempt with all continuing smokers switching to non-menthol cigarettes. Modest decreases occurred in cigarettes smoked per day (11.9 vs. 9.8 cigs/day; p < .001) and exhaled CO (13.4 vs. 11.1 ppm; p = .03) between the start and the end

of the 4 week period. Motivation to quit smoking was higher at the week 4 visit than at baseline (5.3 vs. 6.3 on a 10 point scale; $p = .03$). At the end of the study, subjects indicated that quitting menthol cigarettes was difficult (average score = 7.2 on a 10 point scale) but that they were supportive of banning menthol (average score = 7.1). Our finding of substantial support for a ban on menthol cigarettes is consistent with other surveys^{16, 18} and is important data since broadening support for a menthol cigarette ban among current users of menthol cigarettes would likely ease passage of such regulations. The current study would expand on these data to determine if these changes in smoking, motivation to quit smoking, and other measures assessed are either enhanced or undermined by the availability of menthol flavored e-cigarettes. This study will also provide information regarding the level of support among menthol flavored cigarette smokers of banning menthol flavoring across tobacco products.

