3.0 Study Endpoints/Events/Outcomes

3.1 Primary Endpoint/Event/Outcome: The primary outcome is the amount of each tobacco product used per week as recorded on their tobacco use surveys.

3.2 Secondary Endpoint(s)/Event(s)/Outcome(s): Secondary outcomes measured at each visit include how much of each product is obtained from the experimental marketplace, motivation and self-efficacy to quit smoking cigarettes and to quit all tobacco product use, number of quit attempts, severity of craving and withdrawal symptoms, and exhaled carbon monoxide concentrations. Support for a menthol ban and urinary cotinine concentrations will be assessed at baseline and at week 6.

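### Exhaled CO is compared across visits without controlling or recording visit time or time since the last cigarette, which adds avoidable within-person noise to a secondary outcome

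*Combined protocol and SAP*

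**What the plan says.** Section 3.2 lists "exhaled carbon monoxide concentrations" among the secondary outcomes measured at every visit. Section 5.2.2 takes CO from a breath sample at baseline. For weeks 2, 4 and 6, section 5.2.3 says "At each visit, exhaled carbon monoxide concentrations will be measured and subjects will complete questionnaires". Neither section sets a time of day or asks when the participant last smoked. The daily survey in section 5.2.1 covers products used over the past day and is not described as timing the last cigarette. The mixed model in section 16.1 has group, time, their interaction and a random subject effect, with no term for visit timing.

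At screening the protocol is more careful. Section 5.2.1 requires CO of at least 8 ppm but allows a urine nicotine strip instead for people who otherwise qualify and read lower. Its examples of why this may happen are "they didn't smoke that morning, they came straight from work, etc". That back-up serves eligibility only.

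The CO effect size available in the protocol is the pilot result in section 2.2.1: "exhaled CO (13.4 vs. 11.1 ppm; p = .03".

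**The concern.** The primary outcome is self-reported product use, and participants know which products their marketplace offers. Few planned measures can check reported cigarette counts objectively. Urinary cotinine is a nicotine metabolite, and section 14.1 says that every product supplied contains nicotine, so cotinine cannot separate cigarettes from e-cigarettes, gum or lozenge. Cartridge and vial weights follow e-cigarettes only. Marketplace records show what was obtained, and section 5.2.2 puts no penalty on outside purchases. CO is therefore the only planned biomarker specific to combusted tobacco, the exposure that Aim 1 predicts will fall.

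A participant seen soon after smoking at baseline and after a long gap at week 4 would show a CO fall with no change in smoking habits. If timing is not recorded at the visit, the analyst cannot reliably recover it later. The study is also meant to inform the design of a larger one, so the avoidable noise would carry into any CO variance used for that planning.

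**Working it through.** **1. The plan's own figure.** Section 4.1 states "Subjects will be randomized to one of three experimental marketplaces (20 subjects in each condition". Section 16.2 says the investigators "anticipate (assuming 10% dropout), that there would be 18 evaluable subjects per group" (60 × 0.90 / 3 = 18), and that "this sample size will provide 80% power for a between-groups time-averaged effect size of 0.8", "assuming two-sided alpha=0.05 and within-subject autocorrelation of 0.6". With three post-baseline visits and a common correlation of 0.6, the variance factor for a subject's average is (1 + 2 × 0.6)/3 = 0.733. The standardised difference over its standard error is 0.8 / √(0.733 × 2/18) = 2.80, and 2.80 − 1.96 = 0.84, which gives 80% power. The stated figure is reproduced (77.7% with a t distribution).

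**2. One participant's reading.** From the pilot mean to the screening cut-off is 13.4 − 8 = 5.4 ppm. The pilot group change was 13.4 − 11.1 = 2.3 ppm, and 5.4 / 2.3 = 2.3. A reading that drops below the cut-off has therefore moved by more than 2.3 times the pilot effect.

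**3. What the pilot implies about variability.** Assume the p-value came from a paired t-test on the 32 completers (section 2.2.1). Then t = 2.275 and the SD of the change is 2.3 × √32 / 2.275 = 5.7 ppm. The within-subject visit SD is 5.7/√2 = 4.0 ppm. At a correlation of 0.6 the single-visit SD is 4.04/√0.4 = 6.4 ppm. So 2.3 ppm is 2.3/6.4 = 0.36 SD, while the trial is sized for 0.8 SD, or 0.8 × 6.4 = 5.1 ppm. Section 2.1 gives 31 pilot subjects instead of 32; with 31 the SD of the change is 5.6 ppm, which alters nothing here.

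**4. Power for a pilot-sized difference, 18 per arm, t-based.**
- Three-visit average: SE = 6.4 × √0.733 × √(2/18) = 1.83 ppm; power about 23%.
- Adjusted for baseline: SE = 6.4 × √(0.733 − 0.36) × √(2/18) = 1.30 ppm; power about 40%.
- For correlations of 0.4 to 0.8, these run from 38% to 13% and from 49% to 34%.
- For A and C together against B (36 against 18), they are about 30% and 52% at 0.6.

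Section 16.1 does not say whether the CO contrast uses the baseline value, so both forms are shown.

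**5. Scheduling noise at group level (assumed inputs).** The documents give no figure. Suppose a badly timed visit lowers the reading by 5.4 ppm, independently at a fraction q of visits. The scheduling SD is 5.4 × √(q(1 − q)). Its contribution to the SE of a pairwise contrast is that SD × √(2/(18 × 3)) for the three-visit average, and that SD × √((2/18) × (4/3)) for change from baseline.

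| q | Scheduling SD (ppm) | SE, three-visit average (ppm) | SE, change from baseline (ppm) |
|---|---|---|---|
| 10% | 1.6 | 0.31 | 0.62 |
| 25% | 2.3 | 0.45 | 0.90 |
| 50% | 2.7 | 0.52 | 1.04 |

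**6. What removing it could buy.** If a scheduling SD of 2 to 3 ppm is already inside the pilot variability and were removed entirely, power for 2.3 ppm would go from 23% to 24–25% on the three-visit average, and from 40% to 48–65% with baseline adjustment. If the noise comes on top of the pilot variability, power falls from 23% to about 22%, and from 40% to 31–35%.

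**The case against.** The case for leaving the plan alone has real force. CO is one of several secondary outcomes in a pilot, is not named in either aim's hypotheses, and the pilot reached p = .03 with all its own measurement noise (whether that study controlled timing is not stated). Marketplace records and returned product also bear on cigarette use, though imperfectly.

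Four stronger readings are tempting, and the documents support none of them.

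- A reader might infer that the protocol says CO falls below the cut-off whenever a smoker has not smoked that morning. Section 5.2.1 gives this only as an example of why an otherwise qualifying smoker may read low, at one visit, against an eligibility threshold.
- A reader might infer that scheduling noise swamps a pilot-sized effect. That comparison works only for a single reading. To shift a group mean by 2.3 ppm, timing would have to move in the same direction on average, and nothing suggests it would. The assumed range gives an SE contribution of about 0.3 to 1.0 ppm.
- A reader might infer a biased arm comparison. Arms are randomized and share one visit schedule, and the documents show no mechanism by which visit times would differ by arm. Without one, this is noise.
- A reader might infer that timing explains the low power for CO. Most of the shortfall is sample size: 0.36 SD against the 0.8 SD planned for. On the three-visit average, removing the noise hardly helps.

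What remains is that timing is neither held nor recorded, that the protocol guards against this at screening alone, and that baseline-adjusted CO comparisons could gain from better control.

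**Conclusion.** The point holds as a cheap improvement. The plan compares CO at weeks 0, 2, 4 and 6 without controlling or recording visit time or time since the last cigarette, although it recognises at screening that a genuine smoker may read low for such reasons. The consequence is avoidable within-person noise in CO changes; bias would need visit timing to differ by arm.

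The single-reading size (more than 5.4 ppm against 2.3 ppm) uses only protocol figures. The group-level size is smaller and rests on assumptions: the size and frequency of timing-related drops, their independence between visits, a paired t-test in the pilot, and a common correlation of 0.6 applied to CO. Larger drops, or timing patterns that persist within a person, would add more than shown. The primary outcome and its stated power are not affected.

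**What to change.** In sections 5.2.2 and 5.2.3, schedule each participant's week 2, 4 and 6 visits as close as practical to the same time of day as the baseline visit. At every CO reading, baseline included, record the clock time and the time since the last cigarette.

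In section 16.1, state that time since last cigarette will be used to describe the data and in a sensitivity analysis only. It should not enter the main CO model, because the assigned condition may itself change how recently someone smoked, and adjusting for it could remove part of the effect under study. Tabulating visit times by arm would show whether timing differed.

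The cost is a sentence in the visit procedures, an addition to the visit form and a line in the analysis plan, with no extra visits or samples. The downside is slightly less flexible scheduling. Clock time is only a proxy: someone may come from work at one visit and from a day off at another at the same hour, so part of the noise will remain.
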